7.4.2 Post-Treatment Follow-Up Period

Summaries for the Post-Treatment Follow-up Period will include data obtained more than 3 days after the subject's last dose of study drug with the following exceptions:

- For BMD, TVU/TAU, and MRI assessments, data obtained more than 28 days after the last dose of study drug in the extension study will be included in the summaries during the Post-Treatment Follow-up Period.
- For AH data, data obtained after the last dose of study drug in the extension study will be included in the summaries during the Post-Treatment Follow-up Period.

7.4.3 Details Regarding Visit Windows

For analyses in the Treatment Period in the extension study, time points and corresponding time windows are defined based on the time of exposure to study drug starting from Study Day 1 in the extension study.

The time windows described in this section will not be applied to bleeding assessments including AH data and Uterine Bleeding Questionnaire (UBQ). Rules described in Section 7.4.1 and Section 7.4.2 will be applied prior to defining time windows. Data considered as in the Treatment Period are not considered in the Post-Treatment Follow-up Period as described in Section 7.4.1 and Section 7.4.2. Any data considered as Baseline (see Section 7.1) will not be included in any post-baseline windows.

Table 1 will be used for analyses of endpoints collected monthly in the Treatment Period of the extension study.

Visit	Nominal Day (Study Day)	Time Window (Study Days)
Month 1	28	$> 1 - \leq 42$
Month 2	56	$> 42 - \le 70$
Month 3	84	$> 70 - \le 98$
Month 4	112	$> 98 - \le 126$
Month 5	140	$> 126 - \le 154$
Month 6	168	$> 154 - \le 196$

Table 1.Analysis Time Windows for Non-Bleeding Measurements Collected
Monthly

Table 2 will be used for analyses of endpoints collected every 3 months in the Treatment Period of the extension study. If there is a scheduled Month 1 visit for the endpoint (e.g., PGIC-MB and PGIC-NBUFS), the first subtable will be used. If there is no scheduled Month 1 visit for the endpoint (e.g., TAU/TVU, BMD, urinalysis, apolipoprotein A and B, reflexive TSH, thyroxine-binding globulin (TBG), UFS-QoL), the second subtable will be used.

Table 2.Analysis Time Windows for Non-Bleeding Measurements Collected
Every 3 Months in the Treatment Period

Visit	Nominal Day (Study Day)	Time Window (Study Days)
Month 1	28	> 1 - ≤ 56
Month 3	84	$> 56 - \le 140$
Month 6	168	$> 140 - \le 196$
Visit	Nominal Day (Study Day)	Time Window (Study Days)
Prior to Month 3	28	$> 1 - \le 56$
Month 3	84	$> 56 - \le 140$
Month 6	168	$> 140 - \le 196$

Table 3 will be used for analyses of endpoints collected at Month 6 (biopsy, MRI, creatinine phosphokinase, EQ-5D-5L, WPAI) in the Treatment Period of the extension study.

Table 3.Analysis Time Windows for Non-Bleeding Measurements Collected
Every 6 Months in the Treatment Period

Visit	Nominal Day (Study Day)	Time Window (Study Days)
Prior to Month 6	70	$> 1 - \le 140$
Month 6	168	$> 140 - \le 196$

Table 4 will be used for analyses of endpoints collected at Post-Treatment Month 1, 3, 6, 9, and 12 of the extension study (e.g., vital signs, clinical safety labs including chemistry, hematology, lipid panel and urinalysis, apolipoprotein A and B). Table 5 will be used for analysis of endpoints collected at Post-Treatment Month 3 and 6 of the extension study (e.g., TAU/TVU). Table 6 will be used for analysis of endpoints collected at Post-Treatment Month 3 of the extension study (e.g., MRI). Table 7 will be used for analysis of endpoints collected at Post-Treatment Month 6 and 12 of the extension study (e.g., BMD).

Table 4.Analysis Time Windows for Non-Bleeding Measurements Collected
at Post-Treatment Month 1, 3, 6, 9, 12

	Nominal Day (Study End Day)	Time Window (Study End Days)
Post-Treatment Month 1	28	> 3 - < 42
Post-Treatment Month 3	84	> 42 - ≤ 126
Post-Treatment Month 6	168	$> 126 - \le 210$
Post-Treatment Month 9	252	$> 210 - \le 294$
Post-Treatment Month 12	336	> 294

Table 5.Analysis Time Windows for Non-Bleeding Measurements Collected
at Post-Treatment Month 3 and 6

	Nominal Day (Study End Day)	Time Window (Study End Days)
Post-Treatment Month 3	84	> 28 - ≤ 126
Post-Treatment Month 6	168	$> 126 - \le 210$
Post-Treatment Months 7 – 12	266	> 210

Table 6.Analysis Time Windows for Non-Bleeding Measurements Collected
at Post-Treatment Month 3

	Nominal Day (Study End Day)	Time Window (Study End Days)
Post-Treatment Month 3	84	> 28 - ≤ 126
Post-Treatment Months 4 – 12	224	> 126

Table 7.Analysis Time Windows for Non-Bleeding Measurements Collected
at Post-Treatment Month 6 and 12

	Nominal Day (Study End Day)	Time Window (Study End Days)
Prior to Post-Treatment Month 6	84	$> 28 - \le 140$
Post-Treatment Month 6	168	$> 140 - \le 196$
Post-Treatment Months 7 – 11	252	$> 196 - \le 308$
Post-Treatment Month 12	336	> 308

7.4.4 Handling of Multiple Assessments in a Specific Time Window

For all parameters except MBL volume, multiple assessments in a specific time window will be handled as follows:

- For parameters other than BMD and WPAI data (or otherwise specified), if more than one assessment is included in a time window, then the assessment performed closest to the scheduled study day (i.e., the nominal day) will be used in the analyses. If more than 1 day is of equal proximity to the nominal day, then the data collected after the nominal day will be used in the analyses.
- For BMD data, if multiple assessments exist in a specific time window, analyses of data will be based on the most conservative (worst) assessment.
- For WPAI data, if multiple assessments exist in a specific time window in the treatment period, analyses of data will be based on the last assessment during the treatment period.

7.5 Dealing with Multiple Values on the Same Day

If multiple measurements are made on the same day for a laboratory parameter or a vital signs parameter, the average of the values will be used in analyses. For summaries of shifts from Baseline and potentially significant values, multiple values on the same day will not be averaged; all values will be considered for these analyses.

If multiple measurements for a particular parameter other than a laboratory parameter and a vital signs parameter are made on the same day for the same subject, the most conservative (worst) measurement will be used in analyses.

7.6 Definitions and Conventions of MBL Volume and Bleeding Days

7.6.1 MBL Volume

The MBL volume is based on validated and non-validated sanitary products unless otherwise specified (for some sensitivity analysis, the MBL volume will be based on validated sanitary products only).

7.6.1.1 Observed MBL Volume Over a Window

If there were observed AH data between two study visits (Product Collection Visit or site visit with UBQ completed), then the MBL volume on the days with observed AH data will be the observed AH data and the MBL volume for the rest of days between the two study visits will be imputed as 0 by AH data.

UBQ responses indicate if a subject has any bleeding or spotting since the last study visit (Product Collection Visit or site visit with UBQ completed). If observed evaluable AH data is available over a window, then the UBQ will not be considered.

If the AH data is reported as "NVB" (no visible blood, discarded without assay), "NO BLEED" (no collection due to no bleeding as indicated by subject or clinical site on assay requisition form), or "TL BQL" (total below low limit of quantitation), the numeric value for the AH data will be imputed as 0. If the AH data is reported as other character value ("NULL," "IN ERROR," "NO DATA," and etc.), the corresponding numeric value for the AH data will be set as missing.

The observed MBL volume over a window (such as the Final Month, Month 1 [Study Days 1 – 28], Month 2 [Day 29 – Day 56], Month 3 [Day 57 – Day 84], Month 4 [Day 85 – Day 112], Month 5 [Day 113 – Day 140], and Month 6 [Study Days 141 – 168]) is defined as follows:

- If a subject has any evaluable AH data reported in the window, then the subject's MBL volume in this window will be the total combined observed AH data of validated and non-validated sanitary products over this window.
- If a subject is missing AH data or all AH data are unevaluable in the window and the UBQ is completed and indicates no bleeding or spotting, "Subject only had spotting that did not require the use of sanitary products" or "There was no visible blood on the sanitary products" and covers this window, then:
 - $\circ~$ A value of 0 will be assigned to the MBL volume over this window.
- If a subject is missing AH data or all AH data are unevaluable in the window and the UBQ is completed with no bleeding or spotting or "Subject only had spotting that did not require the use of sanitary products" or "There was no visible blood on the sanitary products" indicated but UBQ does not cover the full window, then:
 - A value of 0 will be assigned to the MBL volume over this window if the days not covered by UBQ response as described above have AH imputed MBL volume (see first paragraph in Section 7.6.1.1) being 0 for those days.

If there is still no value assigned after the imputation procedure described above, the observed MBL volume over the window is considered missing.

7.6.2 Bleeding Days

A bleeding/spotting day is defined as a day having daily MBL volume of > 0 mL.

A spotting day is defined as a day having daily MBL volume of > 0 - 2 mL.

A bleeding day is defined as a day having daily MBL volume of > 2 mL.

Bleeding intensity categories are

- Daily MBL volume of > 2 10 mL.
- Daily MBL volume of > 10 40 mL.
- Daily MBL volume of > 40 80 mL.

• Daily MBL volume of > 80 mL.

Please note that only observed AH data will be used for daily MBL volume categories above.

8.0 Demographics, Baseline Characteristics, Medical History, and Prior/Concomitant Medications

8.1 Demographic and Baseline Characteristics

Demographics and Baseline characteristics will be summarized for all randomized subjects who received at least one dose of study drug by the six analysis groups listed in Section 5.3. The number of missing values will also be summarized.

No statistical tests will be performed.

8.1.1 Demographics

Continuous variables such as age, height, weight, and BMI will be summarized with the mean, standard deviation (SD), median, minimum, and maximum by analysis group. Number and percentage will be computed by analysis group for the following demographic parameters: age group $(18 - < 20 \text{ years old}, 20 - < 25 \text{ years old}, 25 - < 30 \text{ years old}, 30 - < 35 \text{ years old}, 35 - < 40 \text{ years old}, 40 - < 45 \text{ years old}, 45 - < 50 \text{ years old}, \ge 50 \text{ years old}$, BMI ($\le 18.5 \text{ kg/m}^2$, $> 18.5 \text{ kg/m}^2 - < 25 \text{ kg/m}^2$, 25 kg/m^2 , 30 kg/m^2 , 30 kg/m^2 , $- < 30 \text{ kg/m}^2$, 30 kg/m^2 , $- < 35 \text{ kg/m}^2$, $- < 40 \text{ kg/m}^2$, $\ge 40 \text{ kg/m}^2$), sex, race, ethnicity, tobacco use (current, former, never, and unknown), and alcohol use (current, former, never, and unknown).

The number and percentage of subjects with Baseline presence of adenomyosis (as defined in Section 11.3.5.3) will be summarized.

8.1.2 Baseline Characteristics

Menstrual Blood Loss (MBL)

Baseline MBL measured by AH method as defined in Section 7.1 will be summarized with mean, SD, median, minimum, and maximum values.

Bleeding Days

Baseline for bleeding days will be based on the observed daily AH data as defined in Section 7.1 and Section 7.6. The numbers of bleeding days by intensity categories at Baseline will be summarized with mean, SD, median, minimum, and maximum.

Hemoglobin Concentration

Baseline hemoglobin concentration will be summarized with mean, SD, median, minimum, and maximum values. The number and percentage of subjects with Baseline hemoglobin concentration in the following categories will be summarized: $\leq 10.5 \text{ g/dL}$, $> 10.5 - \leq 12 \text{ g/dL}$, and > 12 g/dL.

Fibroid and Uterine Volume

Baseline uterine volume, Baseline volume of the largest fibroid, and Baseline total fibroid volume (3 largest fibroids) will be summarized with mean, SD, median, minimum, and maximum.

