#### **5.2.2.2 Iron Supplementation**

Excessive blood loss from heavy menses may result in iron deficiency anemia. Iron deficiency anemia is defined by the World Health Organization (WHO) as an Hgb concentration below 12 g/dL (120 g/L) for non-pregnant women. Subjects entering the study with anemia or who develop anemia during the study, if not already taking iron supplements, should be prescribed iron supplementation by the Investigator, as per standard of care. If the Investigator does not prescribe iron supplements for subjects with a Hgb < 12g/dL, the reason should be documented in source documents.

The recommended oral dose of ferrous sulfate is 300 to 325 mg following the diagnosis of anemia. If a subject is unable to tolerate ferrous sulfate then ferrous gluconate, liquid iron or intravenous (IV) iron may be prescribed. If subjects experience constipation from iron supplement use, stool softeners may be prescribed. All iron supplements taken during the study must be recorded on the concomitant medications eCRF.

Further instructions on the provision of iron supplementation and stool softeners will be provided separately from this protocol.

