#### **8.1.7.3.2 Hemoglobin Concentration**

The change and percent change from baseline in hemoglobin concentration will be summarized monthly for each treatment group. Shift tables from baseline to values over time will be summarized by anemia status.

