4.3 Sample Size

The two pivotal Studies M12-815 and M12-817 have a planned enrollment of a total of 800 subjects. Based on assumptions related to discontinuation in the pivotal studies and the estimated roll over rate into this extension study, approximately 400 subjects are expected to be enrolled in this extension study.

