11.3 Secondary and Other Efficacy Analyses

Secondary efficacy endpoints during the Treatment Period include the following:

- Change and percent change from Baseline in MBL volume to each month and to the Final Month;
- Percentage of subjects with suppression of bleeding (no bleeding allowed, spotting allowed) at the Final Month;
- Percentage of subjects with Baseline hemoglobin ≤ 10.5 g/dL who have an increase in hemoglobin > 2 g/dL at Month 6.

Other efficacy endpoints during the Treatment Period include the following:

- Percentage of subjects with MBL volume < 80 mL and 50% or greater reduction in MBL volume from Baseline during 28-day intervals throughout the Treatment Period;
- Percentage of subjects with amenorrhea;
- Percentage of subjects with control of bleeding;
- The number of bleeding days;
- Change and percent change from Baseline in hemoglobin concentration;
- Patient Global Impression of Change (PGIC) questionnaire for Menstrual Bleeding and Non-Bleeding Uterine Fibroid Symptoms;

- Change and percent change from baseline in fibroid and uterine volume;
- Change from baseline for the UFS-QoL;
- Change from baseline for the EuroQoL-5D (EQ-5D-5L);
- The Health Care Resource Utilization (HCRU) questionnaire;
- Change from baseline for the WPAI.

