11.3.4 Hemoglobin Concentration

Hemoglobin (Hgb) concentration data will be summarized as observed.

The change and percent change from Baseline in Hgb concentration to Months 1-6 during the Treatment Period will be summarized by analysis group.

The number and percentage of subjects with changes in Hgb concentration from Baseline to Months 1 - 6 during the Treatment Period in each of the following categories will be summarized by analysis group.

- Change from Baseline in Hgb ≤ -1.0 g/dL
- $-1.0 \text{ g/dL} < \text{Change from Baseline in Hgb} \le -0.5 \text{ g/dL}$
- -0.5 g/dL < Change from Baseline in Hgb < 0.5 g/dL
- 0.5 g/dL \leq Change from Baseline in Hgb < 1.0 g/dL
- $1.0 \text{ g/dL} \leq \text{Change from Baseline in Hgb} < 1.5 \text{ g/dL}$
- 1.5 g/dL \leq Change from Baseline in Hgb < 2.0 g/dL
- Change from Baseline in Hgb ≥ 2.0 g/dL

Also, shift tables from Baseline to Month 3 and Month 6 will be summarized by the following categories.

- Hgb ≤ 10.5 g/dL
- $10.5 \text{ g/dL} < \text{Hgb} \le 12 \text{ g/dL}$
- Hgb > 12 g/dL

The number and percentage of subjects who had Hgb Baseline ≤ 10.5 g/dL and have an increase in Hgb concentration > 2 g/dL from Baseline will be summarized for each month by analysis group.

The number and percentage of subjects who had Hgb Baseline ≤ 10.5 g/dL and have an increase in Hgb concentration > 1 g/dL from Baseline will be summarized for each month by analysis group.

In addition, the number and percentage of subjects who have an increase in Hgb concentration > 1 g/dL from Baseline will be summarized for each month by analysis group and Baseline Hgb concentration categories as follows. Same summary will be provided for increase in Hgb concentration > 2 g/dL from Baseline to each month.

- Hgb ≤ 10.5 g/dL
- $10.5 \text{ g/dL} < \text{Hgb} \le 12 \text{ g/dL}$
- Hgb > 12 g/dL

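### The SAP's hemoglobin categories split at ≤ 12 / > 12 g/dL, so a value of exactly 12.0 is grouped with values the protocol calls anemic and the shift tables do not give anemia status as the protocol defines it

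*SAP*

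**What the plan says.** Protocol 5.2.2.2 (Iron Supplementation) gives the definition: "Iron deficiency anemia is defined by the World Health Organization (WHO) as an Hgb concentration below 12 g/dL (120 g/L) for non-pregnant women". The same section uses the strict inequality again for record-keeping: "If the Investigator does not prescribe iron supplements for subjects with a Hgb < 12g/dL, the reason should be documented in source documents". Under both sentences 12.0 g/dL is not anemia.

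Protocol 8.1.7.3.2 then commits to an analysis: "Shift tables from baseline to values over time will be summarized by anemia status".

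SAP 8.1.2 introduces the baseline table with "The number and percentage of subjects with Baseline hemoglobin concentration in the following categories will be summarized" and lists ≤ 10.5, > 10.5 to ≤ 12 and > 12 g/dL. SAP 11.3.4 says "Also, shift tables from Baseline to Month 3 and Month 6 will be summarized by the following categories" and repeats those three. It lists them once more as the baseline strata for reporting rises of more than 1 and more than 2 g/dL. The same cut therefore stands in three lists.

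The secondary hemoglobin endpoint (SAP 11.3, protocol 8.1.7.2) takes women with baseline ≤ 10.5 g/dL "who have an increase in hemoglobin > 2 g/dL at Month 6". It does not use the 12 g/dL cut.

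**The concern.** The protocol's line runs between values below 12 and values of 12 or more. The SAP's line runs between values up to and including 12 and values above 12. The two differ for one reportable value, but that value is the threshold itself.

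The shift tables in SAP 11.3.4 are the only SAP analysis that could deliver the protocol's table by anemia status. As written they cannot, because no boundary separates < 12 from ≥ 12. A reader who knows the protocol's definition will take the top category as free of anemia, and will then misplace every woman at 12.0. The middle category also mixes women below the protocol's threshold with women who are not, and this carries into the tables of rises by baseline category.

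**Working it through.** The documents state no figure on this point, so there is none to reproduce. The check has three steps.

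**1. Boundary values**

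| Hgb (g/dL) | Protocol 5.2.2.2 | SAP 8.1.2 and 11.3.4 |
|---|---|---|
| 11.9 | anemic | > 10.5 to ≤ 12 |
| 12.0 | not anemic | > 10.5 to ≤ 12 |
| 12.1 | not anemic | > 12 |

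Only 12.0 is placed differently.

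**2. Share above the cut at one visit**

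The difference is P(X ≥ 12) − P(X > 12) = P(X = 12.0), which cannot be negative. Its size needs a distribution and a reporting precision, and the documents give neither. Assume reporting to 0.1 g/dL and X ~ N(m, s), so that P(X = 12.0) = Φ((12.05 − m)/s) − Φ((11.95 − m)/s).

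- Over m = 11.5, 12, 12.5, 13 and s = 1.0, 1.3, 1.6 this runs from 2.1% (m = 13, s = 1.6) to 4.0% (m = 12, s = 1.0).
- At m = 12, s = 1.3: 51.5% are at or above 12 and 48.5% are above 12. The difference is about 3 points, or 0.03 × 400 = 12 women if all are pooled (SAP 4.3: "approximately 400 subjects are expected to be enrolled in this extension study"). Efficacy summaries are given by four groups, so the count within any one group is smaller.
- The share is close to the reporting step times the density at 12. With values kept to 0.01 g/dL it would be about a tenth as large.

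**3. Shifts from baseline B to a later value F**

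Protocol cut: count = P(B < 12, F ≥ 12). SAP cut: count = P(B ≤ 12, F > 12). Hence

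SAP − protocol = P(B = 12.0, F > 12) − P(B < 12, F = 12.0).

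The first term adds women who were never anemic. The second drops women who reached exactly 12.0. The sign depends on which is larger. The rate divides each count by its own denominator, P(B < 12) or P(B ≤ 12).

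Assumed inputs: baseline mean 10.5–12.5, SD 1.2–2.0; mean change 0–2, SD of change 0.7 or 1.2, independent of baseline; values to 0.1 g/dL. Some cases, per 400 women:

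| Baseline mean (SD) | Change mean (SD) | Protocol count | Added | Dropped | SAP count | Protocol rate | SAP rate |
|---|---|---|---|---|---|---|---|
| 12 (1.5) | 1 (0.7) | 92.0 | 9.7 | 7.1 | 94.6 | 47.3% | 46.1% |
| 12.5 (1.2) | 2 (0.7) | 116.1 | 12.2 | 2.2 | 126.0 | 89.8% | 89.0% |
| 10.5 (1.5) | 1.5 (0.7) | 138.3 | 6.3 | 9.5 | 135.1 | 41.5% | 39.8% |

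For the first row, P(B < 12) = Φ(−0.05/1.5) = 0.487, or 194.7 women, and P(B ≤ 12) = Φ(0.05/1.5) = 0.513, or 205.3 women. Then 92.0/194.7 = 47.3% and 94.6/205.3 = 46.1%.

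Taking the scenarios with baseline SD 1.5 and every scenario where the SAP count is the higher one, the count moves by about −3 to +10 per 400 and the rate is 0.3 to 1.9 points lower. The remaining scenarios widen this slightly. At baseline mean 10.5 and SD 1.2 the count falls by up to about 5 and the rate by up to about 2.3 points.

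**The case against.** The strongest reply is that the SAP never calls any of these categories anemic. The definition sits in a section on iron supplementation, not in the analysis sections. Protocol 8.1.7.3.2 gives no number for anemia status, and protocol 8.1.7.3 leaves analysis details to the SAP. So the link between the 12 g/dL cut and anemia is an inference. That is fair, but it does not remove the problem. Either the SAP categories are meant as anemia status and the boundary is off, or they are not and the promised table is missing. Both call for an edit.

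The reply is right on two further points. First, little depends on the cut. Hemoglobin is also summarized as change and percent change at Months 1–6, in seven change categories, as rises above 1 and 2 g/dL, and in laboratory shift tables. A boundary shift in one set of descriptive tables cannot hide a hemoglobin response. Second, nothing in the documents ranks correction of anemia as the main consequence of controlling bleeding. Protocol 3.1 says only that heavy bleeding can affect quality of life and may lead to iron-deficiency anemia.

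A reader might also infer that recovery from anemia is under-reported, by around 3 points. The documents do not support this. Neither defines a recovery measure. The 3-point figure is a share at one visit under an assumed distribution, not a shift. Upward-shift counts go either way, and in many plausible cases the SAP cut shows more of them.

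**Conclusion.** The mismatch is real and confined to values of exactly 12.0 g/dL. The SAP tables do not separate anemic from non-anemic women as the protocol defines them.

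The direction is certain for one quantity only. The share read as anemia-free at baseline or at a visit is understated or equal, by about 2 to 4 points under the assumed distribution and 0.1 g/dL reporting. Shift counts may be over- or understated. The rate among women below the cut at baseline is modestly lower, about 0.3 to 1.9 points in most assumed scenarios. All these sizes rest on assumed means, SDs and precision.

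No primary or secondary endpoint, test or sample size uses the cut. This is a low-severity correction, worth making because it is almost free.

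**What to change.** In all three lists (one in SAP 8.1.2, two in SAP 11.3.4) use ≤ 10.5, > 10.5 to < 12, and ≥ 12 g/dL. The 10.5 cut, and with it the secondary endpoint, stays as it is.

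If the sponsor prefers to keep the present cuts, the SAP should state that they are not anemia status and add a shift table at < 12 / ≥ 12 g/dL, so that the commitment in protocol 8.1.7.3.2 is met.

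The first option changes two symbols in each of three lists, six in all. The second adds one sentence and one table. Neither needs new data.
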